### 5.8. Interim Analyses

An interim analysis is planned when approximately 50% of planned Participants reach their Week 12 visit, which is approximately 45 Participants who received at least one administration of study agent (including a partial dose), have completed their Week 12 visit, or have terminated their study participation before Week 12. Additional ad hoc IA(s) may be conducted if deemed necessary. The objective of the IA(s) is to enable early termination of the intervention cohort if JNJ-67864238 is futile and plan for future intervention cohorts. At the time of the IA(s), the study team will remain blinded. No DBL is planned for the IA. The statistical model specified in master protocol Section 9.4.2 and this document Section 5 will be used to evaluate the treatment difference at Week

12 using all available data. The interim analysis criteria are discussed in attachment 1. Interim analyses will be based on data that are as clean as possible.

An internal interim analysis committee independent of the study team will be established to review the interim data and formulate recommended decisions/actions in accordance with predefined decision rules. The details of interim analyses procure will be included in a separate interim analysis plan.

#### Interim Analysis Decision-Making Rules:

If neither change in CDAI nor change in SES-CD of the JNJ-67864238 treatment arm meets the success criteria, the futility of the JNJ-67864238 treatment arm will be considered. The futility is defined as follows:

CCI

CCI

- Futility in change in CDAI: if upper bound (UB) (95%)  $< 60$  and lower bound (LB) (10%)  $< 40$ , ie, the 95% upper confidence bound of the true mean treatment difference at Week 12 is less than 60 and its 90% lower confidence bound less than 40; and
- Futility in change in SES-CD: if UB (95%)  $< 1.6$  and LB (10%)  $< 0.4$ , ie, the 95% upper confidence bound of the true mean treatment difference at Week 12 is less than 1.6 and its 90% lower confidence bound less than 0.4.

If the futility criteria are met, the decision to terminate enrollment will be made based on a benefit risk assessment of the totality of data, including overall efficacy assessments, analysis of biomarker and PD data, and a safety review by the external data monitoring committee (DMC). If the futility criteria are not met and the DMC has not raised any safety issue, enrollment will continue until the planned sample size is reached. To augment decision-making, all available data at this IA, including from those participants without Week 12 assessments, will be analyzed. An Interim Analysis Committee will review the unblinded interim data and formulate recommendations (Section 9.5.1 of the Master protocol PLATFORMPACRD2001).

#### 5.8.1. Data Monitoring Committee (DMC) or Other Review Board

An external DMC will be established to monitor safety data on an ongoing basis to ensure the continuing safety of participants enrolled in the study as noted in Committees Structure in platform protocol Appendix 5, Regulatory, Ethical, and Study Oversight Considerations. Please refer to DMC charter for details.

## 6. SUPPORTING DOCUMENTATION

### 6.1. Appendix 1 List of Abbreviations

5-ASA	5-aminosalicylate
6-MP	6-mercaptopurine
AE	adverse event
ANCOVA	analysis of covariance
AZA	Azathioprine
Bio-IR	biologic intolerant or refractory
Bio-NF	biologic nonfailure, ie, inadequate response to or failed to tolerate corticosteroids or immunomodulators, but not a biologic
CDAI	Crohn's Disease Activity Index
CI	confidence interval
CRF	case report form
CRP	C-reactive protein
DPS	Data presentation specifications
MedDRA	Medical Dictionary for Regulatory Activities
MTX	Methotrexate
SAE	serious adverse event
SAP	Statistical Analysis Plan
SDC	Sponsor Decision Committee
SES-CD	Simple Endoscopic Score for Crohn's Disease
SNP	Single Nucleotide Polymorphism
SSG	Statistical Support Group
TNF	tumor necrosis factor
ISA	Intervention-Specific Appendix
DPS	Data Presentation Specifications
PK	pharmacokinetics
PD	pharmacodynamics
DBL	database lock
DMC	data monitoring committee
IA	interim analysis

## **6.2. Appendix 2 Changes to Protocol-Planned Analyses**

Based on protocol amendment to incorporate COVID-19 infection event, for primary endpoint point analysis, intercurrent events (ICEs) caused by COVID-19 infection will be addressed by treatment police strategy for primary estimator. In addition, hypothetical strategy to assume missing at random after this ICE and tipping point method will be applied to assess the impact after COVID-19 ICEs in a sensitivity analysis as appropriate. Please refer to section 5.3.2 for details. For subject information and safety analyses, COVID-19 infection event will be tabulate in the corresponding tables and listings.

### 6.3. Appendix 3 Demographics and Baseline Characteristics

The number of participants in each analysis set will be summarized and listed by intervention group, and overall. In addition, the distribution of participants by region, country, and site ID will be presented unless otherwise noted.

Table 5 presents a list of the demographic variables that will be summarized by intervention group, and overall. Demographics will also be summarized by region using the full analysis set.

To assess the comparability of participants, the following data will be summarized by treatment group based on the randomized analysis set:

- Participants' demographic data (i.e. age, gender, race, height, weight, and region)
- Baseline disease characteristics (including endoscopic disease), and baseline use and history of Crohn's disease medications
- Medical history of interest

**Table 5: Demographic and Baseline Disease Characteristic Variables**

Continuous Variables:	Summary Type
Age (years)	Descriptive statistics (N, mean, standard deviation [SD], median and range [minimum and maximum], and IQ range).
Weight (kg)	
Height (cm)	
Crohn's Disease Duration (yrs)	
CDAI	
PRO-2 (defined as the sum of the abdominal pain and stool frequency subscores of the CDAI score)	
SES-CD	
CRP Concentration (mg/L)	
Fecal Calprotectin (mg/kg)	
Categorical Variables	
Race ([White, Black or African American, Asian, American Indian or Alaska Native, Native Hawaiian or Other Pacific Islander, Other, Not Reported and Unknown])	
Sex ([Male, Female])	
Involved GI areas ([Ileum only, Colon only, Ileum and colon, Proximal gastrointestinal tract, and Perianal])	
Extra intestinal manifestations ([Absent, Present])	
Endoscopic disease severity (SES-CD score) ([Remission (0-2), Mild inflammation (3-6), Moderate inflammation (7-16) and Severe inflammation (>16)])	
Abnormal CRP (>3 mg/L) ([Yes, No])	
Abnormal fecal calprotectin (>250 mg/kg) ([Yes, No])	
Crohn's disease complications (Intra-abdominal abscess, Sinus tracts /perforation, Fistula, Bowel Strictureing]	

Study Day and Relative Day: Study Day 1 or Day 1 refers to the day of the first study agent administration on or after the randomization date. All efficacy and safety assessments at all visits will be assigned a day relative to this date.

Study day or relative day for a visit is defined as:

- Visit date - (date of Study Day 1) +1, if visit date is  $\geq$  date of Day 1
- Visit date - Date of Day 1, if visit date < date of Day 1

There is no 'Day 0'.

Baseline: Baseline is defined as the last observation prior to the first study agent administration unless otherwise specified.

#### **6.4. Appendix 4 Protocol Deviations**

Major protocol deviations will be summarized by treatment group in the following categories: participants who entered the trial but did not satisfy entry criteria, participants who received the wrong medication or incorrect dose, participants who received disallowed medication, and other as appropriate.

**6.5. Appendix 5 Prior and Concomitant Medications**

Summaries of Crohn's-specific concomitant medications at baseline (including corticosteroids, Immunomodulators, antibiotics and Aminosalicylates) will be summarized.

**6.6. Appendix 6 Medical History**

Medical History will be summarized as needed..

## 6.7. Appendix 7 Intervention Compliance

The number of Participants receiving each scheduled administration will be summarized by treatment group.

Drug compliance is calculated as the percent of number of tablets actually taken during the course of study. Specifically, for patient  $i$

$$Compliance_i = \left( \frac{\text{Actual number of tablets taken}}{\text{Total number of tablets supposed to be taken}} \right) \times 100$$

The number and percentage of patients who completed the specified range of compliance rate, starting at  $\leq 75\%$  compliance to a maximum of 100% in increments of 5% will be summarized by treatment as appropriate. For Participants who discontinue study agent prior to week 12, the expected number of tablets is counted through the time of study agent discontinuation.

## 6.8. Appendix 8 Adverse Events of Special Interest

Adverse Events of Special Interest will be summarized as needed. Any newly identified malignancy or case of active TB occurring after the first study intervention administration(s) in participants participating in this clinical study are considered AEs of special interest.

A **possible Hy's law case** is defined by the occurrence of ALT/AST  $\geq 3$  x the upper limit of normal (ULN), alkaline phosphatase  $< 2$  x ULN together with Tbili  $\geq 2$  x ULN or international normalized ratio  $> 1.5$  (if measured). Any possible Hy's Law case is considered an important medical event and should be reported to the sponsor in an expedited manner using the adverse events of special interest form, even before all other possible causes of liver injury have been excluded ([FDA 2009](#)). A confirmed Hy's law case must be reported as a SAE.

**6.9. Appendix 9 Medications of Special Interest**

Not applicable.

## **6.10. Appendix 10 Laboratory Toxicity Grading**

Laboratory Toxicity Grading related analysis will be performed as needed.

The grading scale use for lab assessments is based on ‘Common Terminology Criteria for Adverse Events (CTCAE) v5.0’.

If a laboratory value falls within the grading as specified below but also within the local laboratory normal limits, the value is considered to be normal and will be reset to grade 0.

Pre-baseline measurements will use the same grading ranges as applied to baseline measurements. In case a test has two sets of ranges – one for baseline normal and one for baseline abnormal, the one for baseline normal will be applied for all measurements taken pre-baseline and on baseline.

## Attachment 1 Decision-Making Framework

There are 2 decision points planned for this ISA protocol:

- At the IA: This IA will take place when approximately 45 participants have completed their Week 12 assessments or have withdrawn from the study before Week 12. If the futility criteria are met, the decision to terminate enrollment will be made based on a benefit risk assessment of the totality of data, including overall efficacy assessments, analysis of biomarker and PD data, and a safety review by the external DMC. If the futility criteria are not met and the DMC has not raised any safety issue, enrollment will continue until the planned sample size is reached. To augment decision-making, all available data at this IA, including from those participants without Week 12 assessments, will be analyzed. An Interim Analysis Committee will review the unblinded interim data and formulate recommendations (Section 9.5.1 of the Master protocol PLATFORMPACRD2001).
- At the completion of this intervention cohort: The overall study success or futility is defined in the Master protocol. This decision-making framework is suggestive but not binding. The final decision will be made based on the totality of data.

### Decision-Making Specifics at the Interim Analysis

If neither change in CDAI nor change in SES-CD of the PTG-200 CCI treatment arm meets the success criteria, the futility of the PTG-200 CCI treatment arm will be considered. The futility is defined as follows:

- Futility in change in CDAI: if upper bound (UB) (95%)  $< 60$  and lower bound (LB) (10%)  $< 40$ , ie, the 95% upper confidence bound of the true mean treatment difference at Week 12 is less than 60 and its 90% lower confidence bound less than 40; and
- Futility in change in SES-CD: if UB (95%)  $< 1.6$  and LB (10%)  $< 0.4$ , ie, the 95% upper confidence bound of the true mean treatment difference at Week 12 is less than 1.6 and its 90% lower confidence bound less than 0.4.

The thresholds chosen for futility at the IA correspond to PTG-200 profile with limited benefit.

### Decision-Making Specifics at the Completion of the Intervention Cohort

The success of the PTG-200 CCI treatment arm is defined as follows:

- Success in change in CDAI: if LB (20%)  $\geq 40$ , ie, the 80% lower confidence bound of the true mean treatment difference at Week 12 is at least 40; or
- Success in change in SES-CD: if LB (20%)  $\geq 0.4$ , ie, the 80% lower confidence bound of the true mean treatment difference at Week 12 is at least 0.4.

The threshold of 40 is selected to provide confidence that a therapy is at least as effective as currently approved therapies (STELARA® [ustekinumab] or adalimumab), where a CDAI change of 40 represents the lower confidence bound for success of the treatment difference between JNJ-67864238 and placebo.

If neither change in CDAI nor change in SES-CD of the PTG-200 CCI treatment arm meets the success criteria, the futility of the PTG-200 CCI treatment arm will be considered. The futility of is defined as follows:

- Futility in change in CDAI: if UB (80%)  $< 60$  and LB (20%)  $< 40$ , ie, the 80% upper confidence bound of the true mean treatment difference at Week 12 is less than 60 and its 80% lower confidence bound less than 40; and
- Futility in change in SES-CD: if UB (90%)  $< 1.6$  and LB (20%)  $< 0.4$ , ie, the 90% upper confidence bound of the true meantreatment difference at Week 12 is less than 1.6 and its 80% lower confidence bound less than 0.4.

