The decision-making framework is applied to a total of 5000 virtual studies with simulated CDAI and change in the Simplified Endoscopic Score for Crohn's disease (SES-CD) data. With 90 participants (54 participants receiving JNJ-67864238 **CCI** [REDACTED] and 36 participants receiving placebo), under the alternative hypothesis, the probability of JNJ-67864238 meeting the success criteria is approximately 87%, and the probability of dropping JNJ-67864238 for futility is approximately 1%. When there is no treatment difference, the probability of JNJ-67864238 meeting the success criteria is approximately 5% and the probability of dropping JNJ-67864238 for futility is approximately 77%. There is approximately a 32% chance that the futility criteria are met at the IA.

For reference, without factoring in the interim futility analysis, the sample size of 90 participants (54 participants in the JNJ-67864238 **CCI** [REDACTED] treatment arm and 36 participants in the placebo treatment arm) will provide 90% power to detect a treatment difference at $\alpha=0.1$ (2-sided) when the true treatment difference is 60 (placebo – JNJ-67864238) in the change in CDAI at Week 12 for both Bio-IR and Bio-NF populations.

Efficacy Analyses

There are no JNJ-67864238-specific efficacy analyses. Refer to the synopsis of the Master protocol PLATFORMPACRD2001 for efficacy analyses.

Safety Analyses

[figure not shown]
There are no JNJ-67864238-specific safety analyses. Refer to the synopsis of the Master protocol PLATFORMPACRD2001 for safety analyses.

Interim Analyses

One IA is planned. It will take place when approximately 45 participants have completed their Week 12 assessments or have withdrawn early from the intervention cohort. Additional ad hoc IA(s) may be conducted if deemed necessary. The objective of the IA(s) is to enable early termination of the intervention cohort if JNJ-67864238 is futile and plan for future intervention cohorts. At the time of the IA(s), the study team will remain blinded. The planned IA (and any additional IA[s]) will be described in the IA SAP.

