9.2.2. Decision-Making Specifics

9.2.2.1. Decision-Making Specifics at the Interim Analysis

If neither change in CDAI nor change in SES-CD of the JNJ-67864238 **CCI** treatment arm meets the success criteria, the futility of the JNJ-67864238 **CCI** treatment arm will be considered. The futility is defined as follows:

- Futility in change in CDAI: if upper bound (UB) (95%) <60 and lower bound (LB) (10%) <40 , ie, the 95% upper confidence bound of the true mean treatment difference at Week 12 is less than 60 and its 90% lower confidence bound less than 40; **and**
- Futility in change in SES-CD: if UB (95%) <1.6 and LB (10%) <0.4 , ie, the 95% upper confidence bound of the true median treatment difference at Week 12 is less than 1.6 and its 90% lower confidence bound less than 0.4.

The thresholds chosen for futility at the IA correspond to an active study intervention profile with limited benefit.

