9.2.2.2. Decision-Making Specifics at the Completion of the Intervention Cohort

The success of the JNJ-67864238 **CCI** treatment arm is defined as follows:

- Success in change in CDAI: if LB (20%) ≥ 40 , ie, the 80% lower confidence bound of the true mean treatment difference at Week 12 is at least 40; **or**
- Success in change in SES-CD: if LB (20%) ≥ 0.4 , ie, the 80% lower confidence bound of the true median treatment difference at Week 12 is at least 0.4.

The threshold of 40 is selected to provide confidence that a therapy is at least as effective as currently approved therapies (STELARA® [ustekinumab] or adalimumab), where a CDAI change of 40 represents the lower confidence bound for success of the treatment difference between JNJ-67864238 and placebo.

If neither change in CDAI nor change in SES-CD of the JNJ-67864238 **CCI** treatment arm meets the success criteria, the futility of the JNJ-67864238 **CCI** treatment arm will be considered. The futility of is defined as follows:

- Futility in change in CDAI: if UB (80%) <60 and LB (20%) <40 , ie, the 80% upper confidence bound of the true mean treatment difference at Week 12 is less than 60 and its 80% lower confidence bound less than 40; and
- Futility in change in SES-CD: if UB (90%) <1.6 and LB (20%) <0.4 , ie, the 90% upper confidence bound of the true median treatment difference at Week 12 is less than 1.6 and its 80% lower confidence bound less than 0.4.

In addition, a decision-making framework based solely on CDAI scores will also be assessed by combining a benefit-risk assessment of the totality of the data, including analyses of biomarker and PD data. For the case of futility criteria based solely on CDAI scores, the UB of 80% based

on a change in the CDAI for the final analysis will be updated to 95% (ie, UB 95% <60) and the LB will remain the same (ie, LB 20% <40). Details will be provided in the SAP.

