9.2.3. Sample Size

9.2.3.1. Operating Characteristics of the Intervention Cohort

The decision-making framework outlined in Section 9.2.2 of this ISA is applied to a total of 5000 virtual studies with simulated CDAI and change in SES-CD data. With 90 participants (54 participants receiving JNJ-67864238 [CC1] and 36 participants receiving placebo), under the alternative hypothesis (Appendix 6 of this ISA, Data Simulation), the probability of JNJ-67864238 meeting the success criteria is approximately 87%, and the probability of dropping JNJ-67864238 for futility is approximately 1%. When there is no treatment difference, the probability of JNJ-67864238 meeting the success criteria is approximately 5% and the probability of dropping JNJ-67864238 for futility is approximately 77%. There is approximately a 32% chance that the futility criteria are met at the IA when there is no treatment difference.

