#### **5.4.1.3. Analysis Methods for the Estimands for the Major Secondary Endpoints**

The major secondary endpoints of clinical remission (either based on CDAI, SES-CD, or PRO-2), clinical response, endoscopic response, and clinical-biomarker response at Week 12 will be compared between PTG-200 group and the placebo group.

A logistic regression model will be used in the responder analyses with the treatment arm and population status (Bio-IR or Bio-NF), if applicable, as fixed factors, at 2-sided significance level of 0.1. In this model, baseline measurements may be included as covariates as appropriate. The change from baseline in the SES-CD score at Week 12 will be evaluated using MMRM model in comparing treatment difference by LS Mean (SD), LS mean (90% CI). P-Value was based on comparison with placebo model. And other statistical analysis as appropriate.

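### The SES-CD decision criteria are on the median difference in the protocol and on the mean in the SAP, with the same thresholds; the change is undeclared and the operating characteristics are not restated

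*SAP*

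**What the plan says.** Protocol 9.2.2.2 defines SES-CD success at the end of the cohort by "the 80% lower confidence bound of the true median treatment difference at Week 12 is at least 0.4". Its final futility rule is also on the median, and for interim futility Section 9.2.2.1 requires that "the 95% upper confidence bound of the true median treatment difference at Week 12 is less than 1.6". In the same lists the CDAI criteria are on the mean.

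The SAP puts every SES-CD criterion on the mean. At the interim (Section 5.8, repeated in Attachment 1) it requires that "the 95% upper confidence bound of the true mean treatment difference at Week 12 is less than 1.6", and at the end that "the 80% lower confidence bound of the true mean treatment difference at Week 12 is at least 0.4". The thresholds (0.4 and 1.6) and the confidence levels are those of the protocol.

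SAP Appendix 2, which should list departures from the protocol, covers only COVID-19 handling ("Based on protocol amendment to incorporate COVID-19 infection event, for primary endpoint point analysis"). SAP 5.4.1.3 plans a mean-based analysis of this endpoint: "The change from baseline in the SES-CD score at Week 12 will be evaluated using MMRM model".

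Operating characteristics appear only in the protocol. Section 9.2.3.1 gives 87% success and 1% futility under the alternative. Under no difference it says that "the probability of JNJ-67864238 meeting the success criteria is approximately 5% and the probability of dropping JNJ-67864238 for futility is approximately 77"%. The synopsis adds "There is approximately a 32% chance that the futility criteria are met at the IA", and Section 9.2.3.1 makes clear that this too is under no difference. SAP Attachment 2 repeats the simulation inputs but gives no results.

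**The concern.** A threshold on a median difference and the same threshold on a mean difference are different rules. Change in SES-CD is simulated as an integer with excess zeros. Bounds from an unaligned Hodges-Lehmann interval are then whole numbers, so a lower bound of at least 0.4 has to be at least 1, and an upper bound below 1.6 can be at most 1. On the mean scale 0.4 and 1.6 apply as written.

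This matters because success is CDAI or SES-CD. If the drug does nothing, the CDAI limb almost never succeeds, so the SES-CD limb sets the false-success rate. Protocol 9.2 and SAP Section 3 both justify the sample size by the behaviour of this framework. A reader of the SAP would take the protocol's 5%, 77% and 32% to describe the rule in the SAP, and would be wrong. The interim recommendation is also meant to follow predefined rules, which at present name two different parameters.

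**Working it through.** **Inputs** (Protocol Appendix 6, SAP Attachment 2): 54 active and 36 placebo; Bio-IR and Bio-NF 50% each. Change in SES-CD, as probability of an excess zero, then mean and SD of the normal part, rounded to an integer:

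- Bio-IR: placebo 32%, -0.22, 3.8; active 19%, -3.26, 3.8.
- Bio-NF: placebo 12%, -2.71, 5.9; active 12%, -4.68, 5.9.

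The SD of change in CDAI is 93 (SAP Section 3). Differences are placebo minus active.

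**Check on the plan's own power.** √(1/54 + 1/36) = 0.2152, so the CDAI standard error is 93 × 0.2152 = 20.0. Power for a difference of 60 at two-sided 0.1 is Φ(60/20.0 − 1.645) = 91%, against the stated 90%.

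**Mean rule, closed form, no difference, no baseline covariate.** With q the probability of a non-zero draw, the variance within a population is q(SD² + mean² + 1/12) − (q·mean)², where 1/12 allows for rounding.

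- Placebo profile in both arms: Bio-IR 9.89, Bio-NF 31.48, average 20.68, SD 4.548. SE = 4.548 × 0.2152 = 0.979. P(80% lower bound ≥ 0.4) = 1 − Φ(0.4/0.979 + 0.842) = **10.6%**.
- Active profile in both arms: 13.40 and 33.02, average 23.21, SD 4.818, SE 1.037; probability **11.0%**.
- CDAI limb: 1 − Φ(40/20.0 + 0.842) = 0.2% (0.3% by simulation).

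**Whole framework by simulation.** Interim at 27/18, final at 54/36. CDAI by ANCOVA with treatment, population and baseline. SES-CD mean by a linear model with treatment and population. One-sided bounds, no dropout, futility considered only if neither success criterion is met. 10,000 trials per scenario for the mean rule and 5,000 for the median rule.

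| % | Success, no diff. | Futility, no diff. | Interim futility, no diff. | Success, alt. | Futility, alt. |
|---|---|---|---|---|---|
| Protocol, stated | 5 | 77 | 32 | 87 | 1 |
| Median, stratified Hodges-Lehmann, placebo-profile null | 4.0 | 77.1 | 29.7 | 85.9 | 1.6 |
| Same, active-profile null | 6.4 | 65.2 | 22.9 | – | – |
| Mean, placebo-profile null | 11.0 | 64.5 | 22.9 | 89.7 | 1.1 |
| Mean, active-profile null | 11.1 | 61.6 | 20.8 | – | – |

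The stratified Hodges-Lehmann rule with the placebo-profile null lies within 2.3 points of every stated figure. A separate simulation of the mean rule gave 10.6–10.9% success, about 65% futility and 22–23% interim futility under no difference.

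**Other median estimators**, 5,000 trials each (success / futility / interim futility under no difference; success under the alternative):

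- Unstratified Hodges-Lehmann: 4.1 / 71.9 / 27.2; 85.0%.
- Hodges-Lehmann aligned on population medians: 5.8 / 71.4 / 27.7; 86.4%.
- Bootstrap difference of arm medians: 2.7 / 79.6 / 30.0; 88.6%.
- Average of within-population median differences: 9.4 / 61.0 / 17.3; 81.3%.

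**If a baseline SES-CD covariate is added to the mean model.** SAP 5.4.1.3 neither names nor excludes one. Suppose baseline explains an assumed 30, 50 or 70% of the variance. Over the two null profiles, 5,000 trials each:

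- false success 8.4–9.7, 7.2–7.9, 4.9–6.2%;
- futility under no difference 72–76, 81–85, 92–93%;
- interim futility under no difference 27–29, 33–35, 44–46%;
- success under the alternative 93, 96, 99%.

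The closed form for false success on the SES-CD limb (placebo profile) agrees: 9.2, 7.8, 5.6%. None of these settings gives the five stated figures together. False success comes near 5% only where futility under no difference is 92–93% and success under the alternative is 99%.

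**The case against.** The size of the gap depends on choices that the documents do not make. The protocol names neither its median estimator nor the profile behind no treatment difference. The whole-number argument holds only for unaligned Hodges-Lehmann-type bounds. A plain difference of arm medians can fall on half-integers, and alignment on population means gives non-integer bounds. With the active profile as the null, a bootstrap difference of medians gave 13.0 / 42.1 / 11.8% in 2,000 trials, which is no better than the mean rule. With a covariate, the mean rule's futility figures fall on both sides of those stated.

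Beyond that, the framework is expressly non-binding, and formal alpha attaches to the hierarchical tests that start with CDAI. The added CDAI-only framework in Protocol 9.2.2.2 does not use SES-CD. The Master protocol and the separate interim analysis plan were not available and may settle the point.

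Most of this stands. It rules out a general statement that moving from median to mean costs a fixed amount, and false success here is not the trial's type I error. It does not remove the conflict between the two documents, nor does it make the stated figures describe the SAP's rule. The fallback to van der Waerden scores in SAP 5.1 does not help either, because bounds on a score scale cannot be compared with 0.4 and 1.6.

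**Conclusion.** The concern holds and should be fixed. The wording conflict is certain: the median in every SES-CD criterion of the protocol, the mean in every one of the SAP, identical thresholds, no declaration and no restated operating characteristics. The mean may be deliberate, since it matches the planned LS-mean analysis, but it is then an undeclared change.

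The size is conditional. With no baseline SES-CD covariate, no dropout and one-sided bounds, false success is about 11% rather than 5%, futility under no difference 62–65% rather than 77%, and interim futility 21–23% rather than 32%. An assumed strong covariate would bring false success down to 5–6% but move the other figures well away from those stated. Under the alternative the mean rule does no worse than stated. The primary CDAI test, its alpha and its power are unaffected.

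**What to change.** Before any unblinded look, use one SES-CD parameter, with a named estimator and interval method, in Protocol 9.2.2.1 and 9.2.2.2, SAP 5.8 and SAP Attachment 1. Check it against the Master protocol and the interim analysis plan.

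- **(a) Restore the median in the SAP.** The cost is SAP wording plus a named median estimator and interval. The SAP should note that the decision rule then differs from the LS-mean analysis in 5.4.1.3.
- **(b) Keep the mean.** Declare it in SAP Appendix 2, state whether baseline SES-CD is a covariate, rerun the existing simulation with that model, and restate the operating characteristics in Protocol 9.2.3.1 and the synopsis. The cost is one rerun and a protocol amendment that also covers 9.2.2. Without a strong covariate, the false-success figure to be published becomes about 11%.

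In either case, state which SES-CD profile represents no treatment difference.
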